7.6. Lost to Follow-up

Subjects that do not complete the scheduled follow-up visits and have not officially withdrawn from the study are considered lost to follow-up; this term does not apply to missed visits. Site personnel should make

considerable effort to locate and communicate with the subject using all available methods (e.g., telephone, emails, and postal mail). The following contact procedure is recommended at each time point:

- A minimum of two telephone calls on different days over the specified follow-up windows should be recorded in the source documentation including date, time, and site personnel initials for the staff attempting to contact the subject.
- If these attempts are unsuccessful, a certified letter should be sent to the subject.
- If the subject misses two consecutive scheduled contact time points and the above mentioned attempts at communicating with the subject are unsuccessful, the subject will be considered lost to follow-up.

While a subject becoming lost-to-follow-up must be considered a possibility, it is imperative that all subjects have the device removed, as the long-term response of the device materials to the stomach environment is not yet known.

8. LIFESTYLE INTERVENTIONS

The goal of the lifestyle modification counseling is to promote use and adherence to a reduced calorie diet (approximately 1500 kcal/d), increase physical activity (primarily through daily walking), and to recommend behavioral modification strategies.

This intervention is adapted from the Brief Lifestyle Counseling condition in the POWER-UP study¹⁶ described previously. A detailed protocol for the lifestyle intervention is attached in Appendix C. Prior to the start of the study, study personnel from the study sites will participate in a training session which will focus on the delivery of the intervention. These study personnel also will participate in ongoing conference calls where they will receive supervision on the delivery of the lifestyle modification intervention to study participants.

8.1. Diet Recommendations

The diet recommendation will follow the recommendations of the Diabetes Prevention Program and as used in the POWER-UP study. Subjects who weigh ≤ 114 kg (≤ 250 lb) will be prescribed 1200-1500 kcal/d and those > 114 kg (> 250 lb) 1500-1800 kcal/d. All subjects will receive the same written information regarding food intake at lifestyle counseling sessions.

8.2. Physical Activity Recommendations

Subjects will be encouraged to increase their physical activity, performing such tasks as taking 10,000 steps a day, avoiding elevators and escalators, etc. No specific methods will be provided to enforce or facilitate subject compliance.

8.3. Behavior Modification

At the same time as the diet prescription and activity advice, subjects will be instructed in behavioral modification strategies to promote weight control and that can be used in their daily lives. Examples of these strategies include reducing food intake by using smaller plates, reducing consumption of high calorie beverages, putting the fork down between bites, etc. These are detailed in the Appendix C.

8.4. Telephone Contacts

In months 7, 8, 10, and 11, when subjects are not scheduled for an in-person follow up visit, subjects will participate in a brief (15-minute) telephone call with study site personnel providing the lifestyle modification counseling. During these calls, subjects will report on changes in weight, dietary intake, eating behavior, and physical activity level. These telephone calls are designed to promote adherence to the lifestyle modification protocol in the absence of in-person visits. The provider will reinforce positive behaviors consistent with the

lifestyle modification program and problem solve issues related to weight gain, increased caloric intake or decreases in physical activity.

9. CONCOMITANT MEDICATIONS

Concomitant medications deemed medically necessary for the subject will be allowed during the course of the study; however, any changes in medications will be documented on the Concomitant Medication Log. Medications used during the placement/removal of the TPS, such as anesthesia, will not be tracked via the Concomitant Medication Log.

9.1. Prohibited Concomitant Medications

9.1.1. Weight-Loss Medications

Study subjects will not be allowed to take any weight-loss products during the course of the study, including prescription, over-the-counter (OTC), and herbal products.

9.1.2. NSAIDs (Non-Steroidal Anti-inflammatory Drugs)

Subjects must be off NSAIDs and aspirin for at least two weeks prior to TPS placement and remain off for the duration of the study. Treatment with Acetaminophen may be continued. Low dose aspirin (81 mg/day) may be used if needed in combination with prophylactic PPI.

9.1.3. Other Medications

Medications affecting subject motility, such as Reglan and Erythromycin should be discouraged, but allowed if necessary.

9.2. Required Concomitant Medications

9.2.1. Proton Pump Inhibitors (PPIs)

Subject will be placed on Omeprazole at 40 mg once daily, or its equivalent starting at least one week before the index procedure and continue for 12 months until the TPS removal (or the last visit in the Control subjects). The dose may be adjusted based on the judgment of the Investigator. Use of the PPIs will be recorded on the Concomitant Medication Log.

10. POST PROCEDURE PATIENT MANAGEMENT

10.1. Managing GI Symptoms

Following the index procedure, the subject should be on liquid diet for three days, followed by soft food for a week, and then slowly return to a normal diet in ten days.

Clinical experience suggest the TPS therapy is well-tolerated by subjects. However, some subjects may experience nausea, vomiting, and bloating after the procedure. Antiemetic (such as Ondansetron) and antispasmodics (such as Butylscopolamine) should be provided on standby, and the subjects should be educated on their use.

In case of prolonged vomiting (more than 4-6 times in 24 hours), subjects should be evaluated and, if necessary, be managed with PO, IV fluid, and intravenous antiemetic.

In case of recurrent vomiting (every day over 3-5 days), abdominal pain, and non-response to medical management, the patient should be evaluated (including endoscopy if necessary) to rule out obstruction or an ulcer.

10.2. Managing Endoscopic Observations

Tissue effects such as erythema, erosions, or ulcers may be observed during endoscopic surveillance. Limited clinical experience to date suggests that some patients may be asymptomatic while others may develop symptoms.

10.2.1. Ulcer Definition

For the purpose of this study, an ulcer is defined as ≥ 5 mm in diameter with unequivocal depth by endoscopy. Ulcer is defined as endoscopically significant if it is ≥ 3 cm in length and ≥ 1 cm in width. Ulcers will be classified as symptomatic or asymptomatic, complicated or uncomplicated. An ulcer is complicated if the patient develops clinical complications including bleeding, perforation or obstruction.

Efforts should be made to capture clear images with an accessory of known dimensions next to the lesion to estimate size.

10.2.2. Guidelines for Managing Endoscopic Observations

The following algorithm (

Figure 13) is suggested for managing endoscopic observations in subjects after the index procedure.

Figure 13. 

10.3. Managing Hypoglycemia Risks in Diabetic Subjects

Subjects with diabetes are potentially at risk of developing hypoglycemia during a weight loss study. The risk may be greatest upon initiation of dietary and device intervention. Among patients with diabetes who qualify for inclusion in this study, the risk of hypoglycemia is very low to absent in those managed with diet alone, and the risk is greater in patients treated with sulfonylureas, repaglinide or nateglinide, than in patients treated with other oral anti-diabetes agents. The following guideline is provided for minimizing severe hypoglycemia in diabetic subjects during the study. The treating physicians should exercise their clinical judgment for the treatment of individual subjects.

10.3.1. Subject Education

At the onset of the study, subjects with T2DM, regardless of diabetic medication regimen, should be educated on the potential for development of hypoglycemia, the symptoms and signs of hypoglycemia, instruction in the use of home blood glucose monitoring to detect hypoglycemia, and instruction on treating hypoglycemia. Symptoms suggestive of hypoglycemia include lightheadedness, tremor, shaking, sweating, tingling, blurred vision, difficulty concentrating, and confusion. With marked hypoglycemia, patients may develop altered consciousness, coma, or seizures. Subjects treated with anti-diabetic medication should self-monitor blood glucose (BG) in the first week post intervention and are encouraged to self-monitor BG throughout the study. Additionally, for subjects treated with sulfonylureas, repaglinide or nateglinide, self-monitoring of BG should be performed twice daily starting one week before the index procedure and continuing for a minimum of 4 weeks post-procedure or until stabilization of glycemic control. Subjects should be instructed to promptly contact site staff for any documented or suspected hypoglycemia.

10.3.2. Subject Management (adapted from algorithms developed and used in the LookAhead Study³²)

During periods of weight loss, subjects who are taking sulfonylureas, repaglinide or nateglinide may need reductions in diabetes medication(s) to reduce their risk of hypoglycemia.

Each diabetic subject should have a treating physician identified for managing subject's diabetic medication during the study. The treating physician maybe the site PI, site clinical staff, or a treating physician not on the study team, in which case the study site will work collaboratively with the subject's non-study treating physician in managing their risks. The treating physician will be responsible for diabetes medication adjustment while the need for medication reduction may be identified by the study subject, research staff, or individual delivering the lifestyle modification intervention.

At the screening visit, subjects who are taking sulfonylureas, repaglinide or nateglinide will be identified by the site. If non-study treating physicians will be responsible for medication adjustment, they will be contacted by the site regarding the plan for glycemic control during the study. Evidence of the treating physician's acknowledgement on a subject's participation in the study will be obtained before a subject's enrollment in the study.

The definition of hypoglycemic episodes can be found in Appendix A. Study subjects or study staff may identify these episodes.

Hypoglycemic Decision Point is defined as one episode of severe hypoglycemia or non-severe hypoglycemia occurring greater than twice weekly. If a Hypoglycemic Decision Point should occur in a study subject, this, should prompt reassessment of the anti-diabetic regimen and reduction or discontinuation of anti-diabetic medications. Before medication changes are made, judgment should be used in determining whether exceptional and/or alterable circumstances are responsible for the low glucose levels (e.g., hypoglycemia attributable to missing a meal or an unusual degree of physical exercise).

10.3.2.1. Prior to Index Procedure

Prior to the start of the study, subjects treated with sulfonylureas, repaglinide or nateglinide medications will be asked to start monitoring blood glucose (BG) at least twice daily (pre-breakfast and pre-supper). After at least one week of BG measurements have been collected, the BG data will be reviewed and used to make decisions on pre-emptively reducing anti-diabetic medication according to the scheme below (**Figure 14**).

Figure 14. 

The above algorithm provides general guidelines for adjustments in doses of sulfonylureas, repaglinide and nateglinide, because of the risk of hypoglycemia associated with their use. The exact adjustments in doses of these medications and also a decision on whether the doses of other anti-diabetic medications should be reduced for individual subjects should be determined by the subject's managing physician based on the overall profile of blood glucose levels, with the goal of reducing the risk of hypoglycemia.

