10.3.2.2. During Study Follow up

Self-monitoring of blood glucose should be performed twice daily for subjects on sulfonylureas, repaglinide and nateglinide medications during the first 4 weeks after the index procedure, and one week before each scheduled visit. For subjects on other anti-diabetic medications, self-monitoring of BG should be performed during the first week after the procedure. Subjects also will be encouraged to measure BG levels at any time that symptoms suggestive of hypoglycemia occur. Additionally, subjects will be asked to promptly report

[figure not shown]
documented or suspected episodes of hypoglycemia to the site staff. Subjects will be referred to the treating physician for medication dose adjustment if they experience one episode of severe hypoglycemia or episodes of non-severe hypoglycemia >2 times per week. Guidelines for medication dose adjustment are provided below (Figure 15).

The process of reviewing BG records by study staff or treating physician should continue until the blood glucose records satisfy the following criteria:

- (1) no ongoing episode of severe hypoglycemia,
- (2) episodes of non-severe hypoglycemia occurring no more often than two times per week, and
- (3) No blood glucose values less than 100 mg/dL.

If the risk of hypoglycemia has not been adequately reduced, doses of sulfonylureas, repaglinide, nateglinide, or possibly other anti-diabetic medication(s) should be further reduced or discontinued if appropriate and in the clinical judgment of the subject's treating physician.

In the event of severe hypoglycemia, study staff will document these episodes on the Adverse Event form.

Figure 15. 

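### The stated start for pre-procedure glucose readings (one week before the index procedure) leaves no whole day for the pre-emptive dose review and generally puts it after the Baseline calorie instruction

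*Combined protocol and SAP*

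**What the plan says.** Section 10.3 of the combined protocol and SAP names users of sulfonylureas, repaglinide or nateglinide as the diabetic subjects at greater risk of hypoglycemia. It adds that risk may peak when diet and device begin.

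- **Start of readings.** Section 10.3.1 gives a date for these users: "self-monitoring of BG should be performed twice daily starting one week before the index procedure". Section 10.3.2.1 also asks them to begin before the study starts, but ties that to no day.
- **Review.** Section 10.3.2.1 then provides: "After at least one week of BG measurements have been collected, the BG data will be reviewed". The purpose is to decide on lowering doses in advance. The exact adjustment "should be determined by the subject's managing physician based on the overall profile of blood glucose levels".
- **Who decides.** Section 10.3.2: "The treating physician maybe the site PI, site clinical staff, or a treating physician not on the study team".
- **Early identification.** Section 10.3.2: "At the screening visit, subjects who are taking sulfonylureas, repaglinide or nateglinide will be identified by the site". Screening may take place up to 8 weeks before the procedure (Section 11.9.1).
- **Diet.** The calorie target is given at the Baseline visit, within the 7 days before the procedure. That visit is not required if screening itself falls within those 7 days (Section 11.9.2).

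**The concern.** The review is a preventive step, meant to lower doses before risk rises in the subjects the protocol singles out. It needs a full week of data and a decision by a physician who may work elsewhere. If readings begin on the stated date, the week of data is complete only as the procedure arrives. By then most subjects will already have been told to restrict calories, which is one of the two moments at which Section 10.3 expects the greatest risk. What is at stake is the timing of one safety step in a small group of subjects. Sample size, alpha, power and the co-primary analyses do not depend on it.

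**Working it through.** The plan states no figure for this interval, so the check is a count of calendar days.

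**Inputs.** Two readings a day, before breakfast and before supper (10.3.2.1). At least 7 days of readings before the review, so 7 × 2 = 14 readings. Start on Day -7 (10.3.1). Baseline visit on Day -7 to Day -1, written as Day -b with b = 1 to 7 (11.9.2). Screening on Day -s with s = 1 to 56 (11.9.1).

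**Stated start, Day -7.**
- First reading before breakfast: the 14th falls before supper on Day -1. Whole days left before Day 0: 0.
- First reading before supper: the 14th falls before breakfast on Day 0. Whole days left: 0.

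**Order relative to the calorie instruction.**
- Breakfast start: the earliest review is on Day -1, which is b − 1 = 0 to 6 days after the Baseline visit.
- Supper start: the earliest review is on Day 0, which is b = 1 to 7 days after it.
- Exceptions: a Baseline visit late on Day -1, after the last reading of a breakfast start, or one on Day 0.

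**Earlier starts, first reading before breakfast.**

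| Start | 14th reading | Whole days left before Day 0 |
|---|---|---|
| Day -7 | Day -1 | 0 |
| Day -8 | Day -2 | 1 |
| Day -10 | Day -4 | 3 |
| Day -14 | Day -8 | 7 |

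Of these, only Day -14 completes the week before the earliest Baseline visit on Day -7. With a supper start on Day -14, the 14th reading falls before breakfast on Day -7 and 6 whole days remain.

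**Room in the screening window.** A 14-day lead requires a delay of 14 − s days when s is below 14.
- s = 14 to 56 (43 days): no delay.
- s = 8 to 13 (6 days): 1 to 6 days.
- s = 1 to 7 (7 days): 7 to 13 days.

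Check: 43 + 6 + 7 = 56. A 14-day interval is well inside the 8-week window.

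**Number affected.** The documents do not give it. As a rough guide, 1 of 20 subjects (5%) in ENDObesity I had Type 2 diabetes (Section 3.4.3). Applied to this trial, 270 × 0.05 = 13.5. The exact 95% interval for 1/20 is 0.13% to 24.9%, or 0.3 to 67 subjects. Eligibility differed in that study, and only the unknown share of diabetic subjects taking these three drug types matters here.

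**The case against.** The strongest reply is that Day -7 is not a limit. Section 10.3.2.1 sets a minimum of one week of readings and no latest start, users are known from screening, and Section 10.3 offers its advice as guidance subject to clinical judgment. That stands: the sections do not contradict each other, and a site that starts early has no problem. The same text nevertheless gives sites one date, and that date is the one that leaves no slack.

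Redaction also limits the point. Figure 14 is the scheme for this very review, and it or Appendix C may hold timing, so the only-dated-start claim covers the visible text alone.

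Three stronger readings are tempting, and the documents do not support them.
- **The review cannot be done before the procedure.** It can be done on the evening of Day -1 or the morning of Day 0, and the treating physician may be the site investigator.
- **The plan breaks its own order by giving diet advice first.** No visible section requires the review to precede the calorie instruction. The argument for that order rests on the statement about risk in Section 10.3.
- **The Baseline waiver permits less than a week of readings.** Section 11.9.2 waives a visit, not the week of readings. The screening visit list also shows no calorie counseling, so on that route only the lack of slack applies.

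Other safeguards remain. Non-study physicians are told of the plan in advance ("they will be contacted by the site regarding the plan for glycemic control during the study"), and "Evidence of the treating physician's acknowledgement on a subject's participation in the study will be obtained before a subject's enrollment in the study". Subjects report suspected episodes promptly, and the Hypoglycemic Decision Point prompts reassessment of the regimen. After the procedure, "The process of reviewing BG records by study staff or treating physician should continue until the blood glucose records satisfy the following criteria". These reduce the consequence, but none of them replaces a dose decision based on the pre-procedure readings.

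A last objection concerns the remedy. A dose cut before the Baseline bloods could shift the glucose and insulin reference values used for secondary endpoints. It could also raise doubt about the criterion of 3 months on a stable oral dose (Section 7.2). Both points are sound, and the fix is ordered to meet them.

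**Conclusion.** The point holds as a timing gap in the visible text. A site that follows the stated date has 0 whole days between the end of the week of readings and the procedure. The review generally comes 0 to 6 days (breakfast start) or 1 to 7 days (supper start) after the calorie instruction, with the exceptions shown above. This rests on three assumptions: the site uses the Day -7 start, the subject has no earlier home readings, and the redacted material gives no earlier date. A reader might infer that these subjects are left unprotected or that trial results are at risk. The documents support neither, because other safeguards operate before and after the procedure and no primary endpoint or analysis is affected. The number of subjects is unknown and probably small. The change is worth making because it is cheap and concerns the subjects at higher risk.

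**What to change.** In Sections 10.3.1 and 10.3.2.1:

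1. Start twice-daily readings for these users at least 14 days before the index procedure.
2. Review the readings with the treating physician at the Baseline visit, after the Baseline blood draw and before the calorie target is given. Document any dose decision before the index procedure. The first full week is normally in hand by Day -8, so readings can go to an outside physician ahead of a late Baseline visit.
3. State that a dose reduction directed by the protocol does not breach the stable-dose inclusion criterion.
4. Where screening replaces the Baseline visit, apply the same 14-day lead and documented review before Day 0. The waiver wording in Section 11.9.2 need not change.

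Dose decisions stay with the treating physician.

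**Cost.** About 7 more days of home readings (7 × 2 = 14) per affected subject. Users screened 14 or more days before the procedure keep their date. The few screened later wait 1 to 13 days longer. If that moves the procedure more than 7 days past screening, a separate Baseline visit is needed. A start on Day -8 or Day -10 would cost less and would give 1 or 3 whole days, but would not put the review ahead of an early Baseline visit.

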10.3.2.2. During Study Follow up

Self-monitoring of blood glucose should be performed twice daily for subjects on sulfonylureas, repaglinide and nateglinide medications during the first 4 weeks after the index procedure, and one week before each scheduled visit. For subjects on other anti-diabetic medications, self-monitoring of BG should be performed during the first week after the procedure. Subjects also will be encouraged to measure BG levels at any time that symptoms suggestive of hypoglycemia occur. Additionally, subjects will be asked to promptly report

[figure not shown]
documented or suspected episodes of hypoglycemia to the site staff. Subjects will be referred to the treating physician for medication dose adjustment if they experience one episode of severe hypoglycemia or episodes of non-severe hypoglycemia >2 times per week. Guidelines for medication dose adjustment are provided below (Figure 15).

The process of reviewing BG records by study staff or treating physician should continue until the blood glucose records satisfy the following criteria:

- (1) no ongoing episode of severe hypoglycemia,
- (2) episodes of non-severe hypoglycemia occurring no more often than two times per week, and
- (3) No blood glucose values less than 100 mg/dL.

If the risk of hypoglycemia has not been adequately reduced, doses of sulfonylureas, repaglinide, nateglinide, or possibly other anti-diabetic medication(s) should be further reduced or discontinued if appropriate and in the clinical judgment of the subject's treating physician.

In the event of severe hypoglycemia, study staff will document these episodes on the Adverse Event form.

Figure 15. 

